#### a. Position of the Investigator:

Faculty or Non-Academic Equivalent  
 Student  
 Staff  
 Resident/Fellow  
 Other

### 4. What type of application is being submitted?

New Study Application (or Amendment/Continuing Review)

### 5. Title Of Study:

Outcomes of topography-guided laser-assisted in situ keratomileusis (LASIK) and phororefractive keratectomy (PRK) compared to wavefront optimized LASIK and PRK

### 6. Study Purposes and Objectives:

**Hypothesis:** Snellen uncorrected distance visual acuity will be the same with wavefront optimized LASIK/PRK treatment compared to topography guided custom ablation LASIK/PRK treatment.

**Objectives:** We aim to conduct a prospective trial comparing the post-operative outcomes in fellow eyes, one of which has undergone wavefront optimized LASIK or PRK treatment and one of which has undergone topography guided LASIK or PRK in order to determine whether equivalent patient visual outcomes are achievable at our institution using both forms of LASIK or PRK treatment.

The outcomes we will measure include uncorrected visual acuity.

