**8. Is there a safety monitoring plan for this study?**

Yes  No

**9. Provide a summary of the statistical methods, data analysis, or data interpretation planned for this study. Factors for determining the proposed sample size (e.g., power) should be stated.**

Standard statistics will be calculated and used to describe the two treatment groups in terms of all study variables. Statistics will be compiled for each variable at the study time points listed in the data collection protocol. Patients withdrawn from the study prior to surgery will not be included in the data analysis and will be replaced in the enrollment group. For eyes that require enhancement surgery, only data collected prior to the enhancement surgery will be included in the statistical analysis.

Power calculations for this study are based on similar prospective, randomized contralateral eye laser refractive studies comparing wavefront optimized and wavefront guided treatments. Previously published contralateral eye studies demonstrated statistically significant results for similar endpoints as our study by including in the range of 70-100 patients for each treatment group. To ensure sufficient patient numbers accounting for 20-30% drop out, including patients that may need enhancement surgery and may not be able to complete the study.

References:

PI: [name]

Submitted: 10/25/2016

**Title:** Outcomes of topography-guided laser-assisted in situ keratomileusis (LASIK) and phororefractive keratectomy (PRK) compared to wavefront optimized LASIK and PRK

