### 2. Describe the potential benefits to society AND to participants (do not include compensation):

This study may not provide direct benefit to participants. We hope this study will help us determine if equivalent patient outcomes are achievable using both FDA-approved forms of LASIK/PRK treatment.

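### The aim is to determine whether fellow-eye visual outcomes are equivalent, but the analysis plan is descriptive by group, with no paired difference, margin, primary visit or decision rule

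*Combined protocol and SAP*

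**What the plan says.** All references are to the Combined protocol and SAP.

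- **Aim.** Under Study Purposes and Objectives, the hypothesis is that "Snellen uncorrected distance visual acuity will be the same with wavefront optimized LASIK/PRK treatment" as with topography-guided treatment. The objective is to "determine whether equivalent patient visual outcomes are achievable at our institution using both forms of LASIK or PRK treatment". Section 6 (Risks and Benefits), item 2, hopes the study will "help us determine if equivalent patient outcomes are achievable using both FDA-approved forms of LASIK/PRK treatment".
- **Design.** Section 4, item 6, randomizes within the patient: one eye to each treatment, with LASIK or PRK the same in both eyes.
- **Outcome.** The same item makes visual acuity primary at the pre-operative and post-operative time points. It does not separate uncorrected from best-corrected acuity. The visit list gives six post-operative visits for uncorrected acuity (Day 1, Week 1, Months 1, 3, 6 and 12) and names none as primary.
- **Analysis.** Section 4, item 9, is the only statistical text: "Standard statistics will be calculated and used to describe the two treatment groups in terms of all study variables" and "Statistics will be compiled for each variable at the study time points listed in the data collection protocol". On enhancement it adds: "For eyes that require enhancement surgery, only data collected prior to the enhancement surgery will be included in the statistical analysis".
- **Size.** Item 9 relies on earlier contralateral-eye studies that "demonstrated statistically significant results for similar endpoints as our study by including in the range of 70-100 patients for each treatment group". The next sentence begins "To ensure sufficient patient numbers accounting for 20-30% drop out, including patients that may need enhancement surgery" and ends without a main clause or a resulting number. Section 3, item 4, gives approximately 400 participants.

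**The concern.** A claim of equivalence needs a statement, made in advance, of how large a difference still counts as equivalent, at which visit, and by what calculation. Item 9 gives none of these. A table of group summaries at six visits cannot by itself confirm or refute the objective. Whoever writes the report must choose the visit, the acuity measure, the method and the criterion with the results in view.

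Two further gaps widen that choice. Summaries by treatment group do not use the within-patient difference, which is what the fellow-eye design was set up to measure. And data collection stops only for the enhanced eye, so after an enhancement one eye of a pair has later data and the other does not. The plan does not say how such a pair is analysed.

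**Working it through.** **1. The plan's own number.** No alpha, power, effect size, SD or margin is given, so no power formula can be run. The visible inputs are 70-100 patients and 20-30% drop out. With N / (1 - drop out):

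- 70 / 0.8 = 87.5, so 88
- 70 / 0.7 = 100
- 100 / 0.8 = 125
- 100 / 0.7 = 142.9, so 143

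The range is 88-143 patients, not about 400. One route does reach 400: 100 patients x 2 eyes x 2 procedures = 400 eyes. But section 3 counts participants, and separate sizing for LASIK and PRK is not described.

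**2. Pairs available.** 400 x 0.7 = 280 and 400 x 0.8 = 320. A count of 400 analysed pairs would require no loss at all.

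**3. Do two natural rules agree?** The SD of the within-patient difference is not in the documents; 0.10, 0.15 and 0.20 logMAR are assumed. A margin of 0.05 and an ordinary paired t-test are also assumptions. Let d be the observed mean difference and s its observed SD, with n = 280 and square root of n = 16.73.

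- Significant at two-sided 5% if |d| > 1.969 x s / 16.73.
- 90% CI inside the margin if |d| < 0.05 - 1.650 x s / 16.73.

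Both hold when |d| lies between 0.0118 and 0.0401 (s = 0.10), 0.0176 and 0.0352 (s = 0.15), or 0.0235 and 0.0303 (s = 0.20). In those ranges one rule says not the same and the other says equivalent. By simulation (2,000,000 replicates, normal data), the chance of this at 280 pairs is:

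| True difference (logMAR) | SD 0.10 | SD 0.15 | SD 0.20 |
|---|---|---|---|
| 0.02 | 92% | 56% | 19% |
| 0.01 | 38% | 20% | 9% |
| 0 | 5% | 5% | 4% |

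**4. The opposite error.** Could a non-significant result be taken for equivalence when the CI does not support it? At n = 280 and s = 0.20, non-significance means |d| <= 0.02353. The CI then reaches at most 0.02353 + 0.01973 = 0.0433, inside 0.05. This holds for every s up to 0.05 x 16.73 / (1.969 + 1.650) = 0.231. The chance is therefore about 0% for all three assumed SDs.

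It rises only under other conditions:

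- Margin 0.03, true difference 0.03, 280-320 pairs: 0% / 1-3% / 19-24% for the three SDs.
- Only 70-100 pairs, margin 0.05, true difference 0.05: about 0% / 4-16% / 25-42%.

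**5. Is the trial large enough?** With a true difference of 0 and 280 pairs, the smallest margin with 90% power for equivalence is about (1.645 + 1.645) x SD / 16.73, which is 0.020 / 0.030 / 0.039 logMAR.

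**The case against.** The strongest reply is that this is a short ethics-board application. On that view, will be the same is an informal null hypothesis, equivalent is everyday language, and an ordinary comparison was intended. Randomized fellow-eye data at six visits would still allow a paired estimate with a CI. Part of this stands. The data will be able to answer the question; what is missing is the advance specification. Rewording the aim as estimation would also remove the mismatch. But item 9 asks for the statistical methods, and the answer names no test of a null hypothesis either, so no decision rule exists on either reading.

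The size of the disagreement in the working depends on the true difference. It is large at 0.02 and small at 0, and the documents give no basis for preferring one value.

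A reader might also infer four stronger things that the documents do not support.

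- *The trial is too small.* With 280-320 pairs and the assumed SDs, margins down to about 0.02-0.04 logMAR are within reach.
- *There is a high risk of declaring equivalence falsely.* At this size with a 0.05 margin, non-significance without a CI inside the margin occurs about 0% of the time. It needs a tighter margin, a larger SD or far fewer pairs.
- *The figure of 400 is an error.* The visible figures do not lead to it, but the sentence that should connect them is incomplete, and whether that lies in the plan or in the text extraction cannot be told.
- *The plan ignores pairing altogether.* The objective does state a fellow-eye comparison; only the analysis section leaves it out.

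**Conclusion.** The point holds as a mismatch between aim and analysis. The objective and the benefits statement seek to determine equivalence in a paired design. The only statistical text plans group-wise description, with no primary visit, within-patient estimate, margin or criterion. Carried out exactly, it yields no result that would establish or reject equivalence. The borrowed size rationale rests on studies that found significant differences and does not address equivalence.

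This should be fixed before the data are seen, but it does not undermine the design or show a shortage of patients. How much the missing rule matters ranges from about 5% conflicting verdicts if the eyes truly do not differ to 19-92% at a true difference of 0.02. Those figures rest on an assumed margin of 0.05, assumed SDs of 0.10-0.20 logMAR, a paired t-test and 280 pairs, none of which the plan states except that 280 follows from its enrolment and upper drop-out figures.

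**What to change.** In section 4, item 9:

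1. Name uncorrected distance acuity in logMAR, at one visit from the existing post-operative schedule, as primary. Align the outcome statement in item 6 with this and make the other visits secondary.
2. Estimate the within-patient mean difference (topography-guided minus wavefront-optimized) with a 90% CI. Declare equivalence only if the whole interval lies inside a margin that the sponsor fixes and justifies before the data are seen. State that a non-significant difference will not be read as equivalence. If no equivalence claim is wanted, reword the aim as estimating the paired difference with its CI.
3. State how a pair is analysed when one eye had enhancement before the primary visit, and add a sensitivity analysis under an alternative rule.
4. Replace the borrowed size rationale with the power or precision that the expected number of analysed pairs (about 280-320 after 20-30% loss) gives for the chosen margin and the sponsor's own SD. Say how about 400 was reached.

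The cost is wording only, with no extra measurements. The sponsor must commit in advance to one margin and one visit. At 280 pairs, a margin below about 0.03 (SD 0.15) or 0.04 (SD 0.20) would leave power under 90%, so whether the number of patients suffices depends on the margin chosen.

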**7. Is this a multi-site study, where more than one site needs IRB approval?**

Yes  No

**8. Background and Introduction:**

In photoablation procedures, an excimer laser is used to sculpt corneal tissue to correct refractive error. During LASIK, a flap of corneal tissue is first created with a femtosecond laser and then the excimer laser is used to ablate the corneal stromal tissue beneath the flap allowing for rapid healing time and visual recovery in addition to a reduction in postoperative pain. In PRK the surface layer of epithelium is removed and then the stromal bed is ablated using the same excimer laser as in LASIK.

The change in shape in the cornea induced by traditional ablation corrects lower order aberrations (LOAs) such as spherical and cylindrical refractive errors or near/far sightedness and astigmatism. Other optical aberrations may be induced by the change in corneal shape associated with the ablation, resulting in light from one point on an object failing to converge onto a single point after passing through the eye's optical system. Following laser refractive surgery for nearsightedness, there is an increase in these optical aberrations that cannot be corrected with spectacles called "higher order aberrations" (HOAs). These higher order aberrations result in degradation of vision and visual phenomena often described as starbursts, haloes, or ghosting of images. This may result in symptoms such as difficulty with night driving, reading, glare and light sensitivity.

To reduce the induction of HOAs, wavefront optimized LASIK/PRK treatments were developed. Wavefront optimized treatments are based on complex optical measurements called aberrometry and have been shown to successfully reduce the number of HOAs using pre-programmed ablation profiles based on population analysis. Wavefront optimized treatments have been FDA approved and widely used for years, including at our institution.

Recently, FDA approval was granted for topography guided custom LASIK and PRK ablation treatments (TCAT). This new type of treatment with the potential to even further reduce HOAs even in very irregular corneas by using a non contact device to establish a map of the corneal surface (corneal topography) in combination with measurements of the pupils. This allows for custom treatments based on measurements conducted on each individual eye.

Wavefront optimized treatments have long been in use at our institution and we have recently acquired the tools for newly FDA approved T CAT treatments using the Allegro Topolyzer (Alcon Surgical, Inc). We propose a prospective comparison of patient visual outcomes after performing wavefront optimized laser refractive surgery in one eye compared to custom topography guided LASIK or PRK in the fellow eye.

**a. Position of the Site Principal Investigator**

Faculty or Non-Academic Equivalent

**b. Will the Site PI consent participants?**  Yes  No

**6. Select HIPAA coverage for this study:**

Study procedures will be conducted within a HIPAA Covered Entity at this site (HIPAA Privacy Rule applies)

7. **Select the study procedures that will be conducted at this site:**

Recruitment

Consent/Enrollment

Research observation/intervention with participants

Data collection

Data analysis

**Do you have an enrollment goal or anticipated enrollment number for this site?**

Yes

No

**Enrollment Number:**

400

8. **Select the University of Utah department responsible for this research:**

OPHTHALMOLOGY AND VISUAL SCIENCE

9. **Add any additional sites that are part of this performance group**

There are no items to display

**3. Participants****1. Ages of Participants:**

18 and older (Consent form needed)

**2. Specific age range of participants (e.g., 7-12 years old, 60+, etc.):**

21 and older

**3. Indicate any vulnerable participant groups (other than children) included:**

None

**If "Other", please specify:****If "None" and no children are involved, answer the following question.****Has the participant selection process overprotected potential subjects who are considered vulnerable so that they are denied opportunities to participate in research?** Yes  No**4. Number of participants to be included and/or enrolled in this entire study, across all study locations:**  
approximately 400**At Utah prior to October 2019:** approximately 400**5. Characteristics of Participants/Inclusion Criteria:**

All subjects who are deemed suitable candidates for laser refractive surgery after routine refractive surgery screening will be considered eligible for participation in this study. Subjects must be at least 21 years of age and not pregnant or nursing (due to fluctuations in visual parameters during pregnancy).

**6. Participant Exclusion Criteria:**

Selection will be consistent with the current standard of care for LASIK or PRK. Any patient who is not a suitable candidate for LASIK or PRK will not be included.

**7. Is a substantial percentage of the participant population anticipated to be non-English speaking?** Yes  No

**Title:** Outcomes of topography-guided laser-assisted in situ keratomileusis (LASIK) and phororefractive keratectomy (PRK) compared to wavefront optimized LASIK and PRK

## 4. Study Information

### 1. Design of Study (select all that apply):

**Non-Experimental and/or Descriptive Research Design:**

There are no items to display

**Experimental and/or Interventional Research Design:**

Prospective Biomedical Intervention or Experiment

Randomized Trial

**Development of a research resource (repositories, databases, etc.)**

There are no items to display

**Other**

### 2. Does your study involve the use of any placebo?

Yes  No

### 3. Length of entire study, from initiation through closeout:

3 years

### 4. How will participants be recruited or identified for inclusion in the study?

a. **Select all methods that will be used:**

In-person contact (e.g., patients, students, etc.)

Written or electronic record review

Written advertising (flyers, brochures, website postings, newspaper ads, etc.)

b. **Describe the recruitment/participant identification process in detail (e.g. who will review charts or records, who can refer participants to the study, where will flyers be posted, how often will recruitment letters be sent, when will follow-up phone calls be made, etc.):**

Patients requesting refractive surgery will be informed about the study and asked if they would like to participate. Advertisements will also be included on the Moran Eye Center website, Facebook page, and Twitter account, as well as in newsprint.

### 5. How will consent be obtained?

Informed Consent Process (with or without a document)

### 6. Describe all the procedures chronologically, from screening/enrollment through study closeout, which will be completed in the research project.

Patients who are interested and eligible to participate in the study will be enrolled and will read and sign the study informed consent prior to surgery.

Participants will have an in depth discussion with our refractive surgery coordinator regarding refractive surgery. Patients will choose LASIK/PRK surgery based on our standard pre-operative discussion that is provided to all patients. As is standard for laser refractive

candidates, the advantages and disadvantages of LASIK/PRK compared to the other refractive surgical options will be discussed.

Following patient selection of their preferred type of refractive procedure they will be randomized as discussed below, and only patients who elect for LASIK/PRK will be included in our study.

Prior to surgery, one eye from each patient will be randomly assigned to receive either Wavefront optimized or Topography Guided treatment. Each patient in the study will have a fellow eye enrolled in the other treatment group. Patients will either receive LASIK treatment or PRK treatment in both eyes but the eyes will be randomized to topography guided or wavefront optimized forms of treatment.

All surgical procedures will be performed according to the standard of care and the surgeons' standard practices. The study outcome measures are standard of care for pre-operative and post-operative evaluation of refractive surgery patients.

The primary outcome measures will be visual acuity at the pre-operative and post-operative and post-operative time points.

Study outcome measures will be evaluated for each treated eye of each subject at each study time point. Additional examinations between study time points may be performed as necessary according to the surgeon's usual care, but will not be considered part of the study data. Patients have a right to withdraw at any time and future medical care will not be influenced by their lack of participation.

If enhancement surgery is deemed necessary and performed during the one-year post-operative period, study data collection will end for that eye at the time of the enhancement. All prior collected data will be included in the statistical analysis.

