**Eyes will be evaluated with the following standard of care procedures:**

- pupil size measured in mesopic format: pre-operative only
- corneal pachymetry: pre-operative only
- uncorrected visual acuity: pre-operatively and post-operative Day 1 (+1 day), Week 1 (+/- 3 days), Month 1 (+/- 10 days), Month 3 (+/- 1 month), Month 6 (+/- 1 month) and Month 12 (+/- 1 month).
- best corrected visual acuity and manifest refraction: pre-operatively and post-operative Month 1 (+/- 10 days), Month 3 (+/- 1 month), Month 6 (+/- 1 month) and Month 12 (+/- 1 month)

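### The fellow-eye comparison of post-operative uncorrected acuity leaves out pre-operative best corrected acuity, a baseline already collected that would remove avoidable noise at no cost

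*Combined protocol and SAP*

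**What the plan says.** The hypothesis (Study Purposes and Objectives) is that "Snellen uncorrected distance visual acuity will be the same with wavefront optimized LASIK/PRK treatment compared to topography guided custom ablation LASIK/PRK treatment". The objectives add only that "The outcomes we will measure include uncorrected visual acuity". The procedures (4. Study Information, item 6) state: "The primary outcome measures will be visual acuity at the pre-operative and post-operative and post-operative time points". That sentence does not say which acuity is meant, names no single time point and gives the pre-operative value no role of its own.

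The design is paired: "one eye from each patient will be randomly assigned to receive either Wavefront optimized or Topography Guided treatment", and the fellow eye receives the other treatment.

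The list of standard-of-care evaluations in the same item includes both measures before surgery: "uncorrected visual acuity: pre-operatively and post-operative Day 1 (+1 day), Week 1 (+/- 3 days), Month 1 (+/- 10 days" and "best corrected visual acuity and manifest refraction: pre-operatively and post-operative Month 1 (+/- 10 days".

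The only analysis text (item 9) says "Standard statistics will be calculated and used to describe the two treatment groups in terms of all study variables", compiled for each variable at each time point. It names no paired model, covariate or baseline. The inclusion criteria (3. Participants, item 5) say "All subjects who are deemed suitable candidates for laser refractive surgery after routine refractive surgery screening will be considered eligible", with an age minimum and no pregnancy or nursing. Neither they nor the exclusion criteria state a limit on best corrected acuity or on the difference between a patient's eyes.

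**The concern.** Pairing removes the visual potential that a patient's two eyes share. It does not remove the part by which they differ. An eye that saw slightly less well than its fellow with best correction before surgery is likely to see slightly less well without correction afterwards, whichever profile it received. That inherited difference enters the treatment contrast unless the analysis accounts for it.

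The pre-operative acuity named in the primary outcome does not solve this. Uncorrected acuity before surgery mostly reflects the size of the refractive error that the laser is meant to remove, so it is a poor guide to potential. Even if the sentence is read to cover best corrected acuity, the value appears there as an outcome and not as a baseline, and treatment cannot affect a measurement taken before surgery.

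At stake is precision. The aim is to show that the two treatments give the same result, and such a claim is only as good as the confidence interval is narrow.

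**Working it through.** **The plan's own figure.** There is none to reproduce. The documents give no SD, correlation, effect size, alpha, power or margin for acuity. What follows is an assumed range.

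**Inputs from the documents.** About 400 participants (3. Participants, item 4) and 20-30% dropout (4. Study Information, item 9). At 30% dropout, 400 × 0.70 = 280 completers. The 70 used below is the low end of the 70-100 patients per group that item 9 takes from earlier studies.

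**Assumed inputs (logMAR).**
- s: SD of the true fellow-eye difference in potential, from 0.02 to 0.08.
- m: measurement error SD per eye, 0.03, with 0.05 as a variant.
- Residual refraction: a half-normal effect per eye with scale 0.08, so its variance is 0.08² × (1 − 2/π) = 0.002326.
- p: share of patients with one eye worse by 0.3 (3 lines), 0 or 2%.
- One letter = 0.02 logMAR.

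**Formulas.** Take each difference as the topography-guided eye minus the wavefront-optimized eye. D_pre is the difference in pre-operative best corrected acuity and D_post the difference in post-operative uncorrected acuity. Let v = s² + p × 0.3².
- Var(D_pre) = v + 2m²
- Var(D_post) = v + 2m² + 2 × 0.002326
- Cov(D_pre, D_post) = v
- Share of variance removed by regression: r² = v² / [Var(D_pre) × Var(D_post)]
- Variance of a change score: Var(D_pre) + Var(D_post) − 2v
- 95% half-width: 1.96 × √(variance / n)

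**Middle case (s = 0.06, m = 0.03, p = 0).** v = 0.0036, Var(D_pre) = 0.0054 and Var(D_post) = 0.01005. Then r² = 0.0036² / (0.0054 × 0.01005) = 0.239. At n = 280 the half-width is 1.96 × √(0.01005/280) = 0.0117 unadjusted and 1.96 × √(0.00765/280) = 0.0102 adjusted. The gain is 0.0015, under a tenth of a letter.

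**Across the range (m = 0.03).**

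| s | p | Var(D_post) | variance removed | half-width at 280, unadjusted → adjusted |
|---|---|---|---|---|
| 0.02 | 0 | 0.00685 | 1% | 0.0097 → 0.0096 |
| 0.03 | 0 | 0.00735 | 4% | 0.0100 → 0.0098 |
| 0.04 | 0 | 0.00805 | 9% | 0.0105 → 0.0100 |
| 0.06 | 0 | 0.01005 | 24% | 0.0117 → 0.0102 |
| 0.08 | 0 | 0.01285 | 39% | 0.0133 → 0.0104 |
| 0.04 | 2% | 0.00985 | 23% | 0.0116 → 0.0102 |
| 0.06 | 2% | 0.01185 | 34% | 0.0128 → 0.0103 |
| 0.08 | 2% | 0.01465 | 46% | 0.0142 → 0.0104 |

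The last row is a gain of about 0.0037 logMAR, or 0.2 letter. With only 70 completers, the middle case goes from 0.0235 to 0.0205, or 0.15 letter.

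**Noisier measurement.** With m = 0.05 and p = 0, the reductions at s = 0.04, 0.06 and 0.08 fall to 3%, 11% and 22%.

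**Bias check.** In a simulation with no treatment effect (100 pairs, SD of D_pre 0.06, residual SD 0.08, slope 1, 4,000 repetitions), the mean estimate was about 0.000 both ways. The standard error was 0.0100 unadjusted and 0.0081 adjusted.

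**Change score against regression.** At s = 0.04, m = 0.03 and p = 0, subtracting pre-operative best corrected acuity gives 0.0034 + 0.00805 − 0.0032 = 0.00825. That is above the unadjusted 0.00805, so subtraction can lose precision where regression does not.

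**The case against.** The strongest reply is that the loss is one of efficiency only and is small at this trial's size. That stands: with 280 completers the half-width is between about half a letter and three-quarters of a letter with or without adjustment. The relative figures (39% of variance at s = 0.08) should not be read as a large practical shortfall.

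The inputs are also assumptions. If most candidates have nearly equal best corrected acuity in the two eyes, the gain is close to nil, and noisier Snellen measurement shrinks it further. This stands too, which is why the range starts at 1%.

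The plan describes all study variables by group, so pre-operative best corrected acuity would be tabulated and an imbalance between arms would be visible. That is true, but a table does not remove the difference from the treatment estimate.

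Finally, item 9 names no test, paired model, primary time point or margin, and that is a larger gap. The present point fits naturally inside the text that would fill it. It remains a specific choice of method, using data already in hand.

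Three stronger readings are tempting, and the documents support none of them:
- **That the comparison is biased.** It is not. The eye is randomised within patient, so unequal potential averages out.
- **That pre-operative best corrected acuity fixes what an eye can reach.** The Background describes aberrations that spectacles cannot correct and a topography-guided treatment that may reduce them, so it is a likely predictor and not a ceiling.
- **That patients with an amblyopic eye will enter and drive the result.** No limit is written, but eligibility defers to routine screening, and the documents do not say whom that screening turns away. The 2% share is purely illustrative.

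**Conclusion.** The point holds as a matter of precision. The plan collects the natural baseline for its outcome and does not use it in the treatment comparison, so any fellow-eye difference in potential remains as avoidable noise. There is no bias. Under the stated assumptions with 0.03 logMAR measurement error, regression removes about 1% (inter-eye SD 0.02) to 39% (SD 0.08) of the paired-difference variance, and 46% in the setting with SD 0.08 and 2% of patients markedly unequal. At 280 completers the interval half-width narrows by roughly 0.1 to 0.2 letter from the middle case upwards, and negligibly at the bottom of the range. The size rests wholly on assumed SDs and on the assumption that pre-operative best corrected acuity predicts post-operative uncorrected acuity. The recommendation does not depend on the exact size, because the adjustment needs no new data and has essentially no downside at this sample size.

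**What to change.** In 4. Study Information, items 6 and 9, state the following before any outcome data are analysed:

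1. The treatment effect is the within-patient difference in post-operative uncorrected acuity on the logMAR scale, topography-guided eye minus wavefront-optimized eye, at the time point the plan names as primary.
2. It is estimated as the intercept of a regression of that difference on the within-patient difference in pre-operative best corrected acuity, taken in the same direction. The covariate must not be centred at its sample mean, because the intercept would then return the unadjusted mean.
3. This is regression adjustment and not a change score.
4. Pre-operative acuity is a baseline measurement and is removed from the primary outcome measures.

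Optionally, report by arm the share of eyes whose post-operative uncorrected acuity equals or betters their own pre-operative best corrected acuity.

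The cost is wording and a Snellen-to-logMAR conversion. Both acuities are already scheduled, so no visit, test or patient is added.
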